XXXX	XXXXXX	XXXXX	XXXXXX	XXXXXX	****	XXXXXXX	XXXXXX	XXXX	****

STATKING Clinical Services (DD-MMM-YYYY) Source Program: xxxxxx.sas

Page x of y

Data Listing 24. Study Drug Administration Data Listing Navidea Biopharmaceuticals - Study No. NAV3-33 Safety Population (N=xxx)

Patient No.	Date/ Time of Injection	Anatomic Location of Injection	Pre-Injection Radioactivity (mCi)/Time of Measurement	Post- Injection Radioactivity (mCi)/Time of Measurement	Calculated Amount of Administered Radioactivity (mCi)	Calculated Mass Dose (µg)	Volume Injected (mL)	Lot Number
XXXX	xxxxxxxx/ xxxx	XXXXXXXX	xxx/ xxxx	xxx/ xxxx	XXX	XXX	XXX	XXX
XXXX	xxxxxxxxx/ xxxx	*****	xxx/ xxxx	xxx/ xxxx	xxx	XXX	XXX	XXX
	xxxxxxxxx/ xxxxx	*****	xxx/ xxxx	xxx/ xxxx	XXX	XXX	XXX	XXX

Data Listing 25. Post-Injection Imaging Data Listing Navidea Biopharmaceuticals - Study No. NAV3-33 Safety Population (N=xxx)

Patient No.	Visit	Date of Imaging	Start Time of Imaging	SPECT/CT Image Finding
XXXX	*****	XXXXXX	xx:xx	XXX
XXXX	*****	XXXXXX	xx:xx	XXX

Data Listing 26. SPECT/CT Reader Results Data Listing - Hands and Wrists Navidea Biopharmaceuticals - Study No. NAV3-33 Safety Population (N=xxx)

Patient	Post-Injection		SPECT/CT
No.	Imaging Time Point	Joint	Image Finding
XXXX	XXXXXXX	XXXXXXXXXXXX	XXXX
		XXXXXXXXXXXX	
XXXX	XXXXXXX	XXXXXXXXXXXX	XXXX
		XXXXXXXXXXXX	

Data Listing 27. TUV Data Listing Navidea Biopharmaceuticals - Study No. NAV3-33 Safety Population (N=xxx)

		TUV Classification of Improvement					
Patient No.	Reader No.	Algorithms Predicting Improvement ^a	Algorithms Predicting No Improvement ^a	Visit	Date/Time	Region of Interest ^b	TUV
XXXX	X	X, X	X	XXXXXXX	XXXXXX	XXXXXX	XXXXX
				XXXXXXX	XXXXXX	XXXXXX	XXXXX
				XXXXXXX	XXXXXX	XXXXXX	XXXXX
				XXXXXXX	XXXXXX	XXXXXX	XXXXX
				XXXXXXX	XXXXXX	XXXXXX	XXXXX
XXXX	X	X	x, x	XXXXXXX	XXXXXX	XXXXXX	XXXXX

^a 1 = Change in Global TUV[5w] Bucketing, 2 = Change in Global TUV[12w] Bucketing
^b Region of Interest is joint or Global.
STATKING Clinical Services (DD-MMM-YYYY)

Source Program: xxxxxxx.sas

Data Listing 28. Qualitative Assessment Data Listing Navidea Biopharmaceuticals - Study No. NAV3-33 Safety Population (N=xxx)

Patient No.	Reader No.	Qualitative Assessment ^a	Date/Time
XXXX	x	XXXXXXX	xxxxxxxx/
XXXX	Х	XXXXXXX	xxxxxxxx/ xxxx

^a Qualitative Assessment is either "Improved" or "Not Improved." STATKING Clinical Services (DD-MMM-YYYY) Source Program: xxxxxx.sas

Data Listing 29. Qualitative plus Quantitative Assessments which differ from Original Quantitative Assessment Navidea Biopharmaceuticals - Study No. NAV3-33 Safety Population (N=xxx)

		Qualitative plus Quantitative	Date/Time of Qualitative plus Quantitative	Original Quantitative	Date/Time of Original Quantitative
Patient No.	Reader No.	Assessment ^a	Assessment	Assessment ^a	Assessment
XXXX	x	XXXXXXX	xxxxxxx/	XXXXXX	 xxxxxxxx/
			XXXX		XXXX
XXXX	х	XXXXXXX	xxxxxxxx/	XXXXXX	xxxxxxxx/
			XXXX		XXXX

^a Assessment is either "Improved" or "Not Improved." STATKING Clinical Services (DD-MMM-YYYY) Source Program: xxxxxx.sas

Data Listing 30. ACR Response Criteria Data Listing Navidea Biopharmaceuticals - Study No. NAV3-33 Safety Population (N=xxx)

Patient		Highest ACR Response	Number of Tender	Number of Swollen	Patient Global	Physician Global		VAS Pain	
No.	Visit	Assessment ^a	Joints	Joints	Assessment	Assessment	HAQ Total	Score	ESR
XXXX	XXXXXXX	XXXXX	XXX	XXX	XXX	XXX	XXX	XXX	XXX
XXXX	XXXXXXX	XXXXX	XXX	xxx	xxx	XXX	XXX	XXX	XXX

^a Options are None, ACR20, ACR50, or ACR70. Response assessment will be blank for baseline measurements. STATKING Clinical Services (DD-MMM-YYYY) Source Program: xxxxxxx.sas

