	• To evaluate the negative predictive value (NPV) of TUV_{global} obtained before initiation of anti-TNF α therapy ($TUV_{global[b]}$) relative to a clinical non-response to therapy at 24 weeks.		
	Secondary		
	• To evaluate the sensitivity and specificity of TUV _{global} obtained before initiation of anti-TNFa therapy and at 5 weeks ± 1 week following change in therapy relative to a positive clinical response or a non-response to therapy at 12 weeks.		
	• To evaluate the NPV of TUV _{global[b]} relative to a clinical non-response to therapy at 12 weeks.		
	• To evaluate the positive predictive value (PPV), negative predictive value (NPV), and overall accuracy (OA) of TUV _{global} obtained before initiation of anti-TNFα therapy and at 5 weeks ± 1 week (ΔTUVglobal _[5w]) following change in therapy relative to a positive clinical response or a non-response to therapy at 12 and/or 24 weeks.		

Confidential Page 7 of 89

Dose(s) and Route of administration	Dose: Tilmanocept will be administered at a mass dose of 150 mcg radiolabeled with 10 mCi Tc 99m. Route of Administration: Tc 99m tilmanocept will be administered through an intravenous (IV) route of administration using a single syringe injected as a slow IV push. The preferred site of IV placement will be the left or right antecubital vein. At the completion of Tc 99m tilmanocept administration, a 10 mL sterile normal saline flush will be administered.		
Study drug	Technetium Tc 99m tilmanocept		
Duration of treatment	24 ± 1 weeks; Tc 99m tilmanocept will be administered at baseline and at Week 5. Tilmanocept will also be administered to a subset of subjects at weeks 12 and 24 (those enrolled and completing Weeks 12 and 24 prior to activation of Amendment 4).		
	 To evaluate sensitivity and specificity in patient subgroups. To evaluate the safety of IV-administered tilmanocept radiolabeled with Tc 99m. 		
	To evaluate the correlation of changes with TUV _{global} and changes in clinical RA assessments as a means to monitor therapy. The state of the correlation of changes with TUV _{global} and changes in clinical RA assessments as a means to monitor therapy.		
	• To evaluate the correlation of changes in TUV _{global} obtained before initiation of anti-TNFα therapy and at 5 weeks ± 1 week following a change in therapy with changes in clinical assessments at 12 and/or 24 weeks for specific anti-TNFα bDMARD agents.		

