tilmanocept radiolabeled with 10 mCi of Tc 99m and undergo baseline planar imaging of the bilateral hands and wrists beginning 60-75 minutes following Tc 99m tilmanocept administration. Upon completion of baseline imaging procedures, subjects will commence a new anti-TNFa bDMARD treatment regimen and return to the clinic 5 ± 1 weeks later for a series of rheumatological evaluations (including CDAI, DAS28, ACR Response Criteria, and HAQ-DI[©]), drug administration, and bilateral hand/wrist imaging. The rheumatological evaluations will be repeated at 12 ± 1 weeks and 24 ± 1 weeks after commencement of the new therapy. Images will undergo centralized quantification for the derivation of joint-specific and global tilmanocept uptake values (TUV). At the joint level, TUV joint is defined as the intra-patient ratio of the average pixel intensity of a joint to the average pixel intensity of the reference region. TUV_{global} is a per patient summary of TUV_{joint} values greater than the upper limit of the 95% prediction interval of the joint-and-viewspecific TUV in the normative database representing RA-specific inflammation. TUV calculations are additionally described in the Statistical Analysis Plan. All images will be read by three nuclear medicine specialists trained in the reading of these images. Each reader will work independently of the other readers and will be blinded to clinical assessments. Each reader will provide both a qualitative read and map regions of interest for calculation of TUVs. Temporal differences in TUV_{global} from baseline to 5 \pm 1 weeks of therapy (\Delta TUV global[5w]) will be compared with longitudinal clinical outcomes at 12 ± 1 and 24 ± 1 weeks of therapy defined by changes in CDAI (ΔCDAI_{12/24w}), changes in DAS28 (ΔDAS28[12/24w]), and assessment of ACR Response Criteria (ACR_{12/24w}) to evaluate the efficacy of TUV_{global} for the accelerated prediction of clinical response to antirheumatic

Planned study dates
Start of study
recruitment/February
2022
End of Recruitment/October
2024
End of Study/May 2025

drugs.

Planned number of study centers

Up to 50 centers in the United States

Number of subjects	198 to 672 evaluable subjects may be enrolled. Details of sample size calculations are further described in Statistical Methods below.	
Efficacy Assessments	Primary endpoints:	
Effect Pissessificines	 Specificity of ΔTUV_{global[5w]} bucketing with respect to ACR50 at week 24. 	

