8.4 Image Acquisition

8.4.1 Planar Scintigraphy

Planar spot views of the hands and wrists will be acquired beginning 60 to 75 minutes post injection at Visits 2 and 4. Images and results derived from the images are investigational and should not be used for clinical decision making or shared with the participant.

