- To evaluate the additive effect of either quantitative or qualitative assessment of Tc 99m tilmanocept imaging to the other at baseline and change from baseline to 5 weeks \pm 1 week to predict clinical response or non-response following a change in anti-TNF α therapy.
- To evaluate the correlation of changes in TUV_{global} obtained before initiation of anti-TNFα therapy and at 5 weeks ± 1 week following a change in therapy with changes in composite clinical assessments and their constituent parameters at 12 and/or 24 weeks.
- To evaluate the correlation of changes in TUV_{global} obtained before initiation of anti-TNF α therapy and at 5 weeks ± 1 week following a change in therapy with changes in clinical assessments at 12 and/or 24 weeks for specific anti-TNF α bDMARD agents.
- To evaluate the ability of changes in TUV_{global} obtained before initiation of anti-TNF α therapy and at 12 weeks ± 1 week following change in therapy to accurately predict a clinical response or non-response at 24 weeks.
- To evaluate the correlation of changes with TUV_{global} and changes in clinical RA assessments as a means to monitor therapy.
- To evaluate sensitivity and specificity in patient subgroups.

• To evaluate the safety of IV-administered tilmanocept radiolabeled with Tc 99m.

The statistical endpoints that address these objectives are defined in Section 4 (efficacy) and Section 5 (safety). Refer to Section 2.2.1 for subgroup definitions and considerations.

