2.5 Calculation of TUV

TUV_{joint} is defined to be the mean pixel intensity of the region of interest (ROI) defined by the reader divided by the mean pixel intensity of the hand reference region. Each of the three blinded readers will have determined the TUV distribution for both anterior and posterior views of the wrists and hands (wrists, MCPs, and PIPs) for the healthy patient normative data set. For all of the following calculations, the reader-specific TUV_{joint} limits will be used. The upper

limit of normal is defined to be the upper limit of the 95% prediction interval of the joint-and-view-specific TUV in the normative data set.

For each RA patient do the following.

Step 1: Calculate TUV_{joint} for each of the 22 DAS28 joints for which data are collected.

Step 2: Identify all imaged joints with $TUV_{joint} > upper limit of normal for the anatomically similar joint and view. These will be referred to as inflamed joints (IJ). Each joint has an anterior and posterior view: a joint is considered an IJ if either view has a <math>TUV_{joint}$ higher than the upper bound from the normative data set.

Step 3: Calculate the macrophage-involved contribution (MI) to Tc 99m tilmanocept localization for each IJ. This is done by expressing the TUV for the IJ as a fractional change from the mean TUV for the anatomically equivalent joint and view. That is, if TUV_{joint} and \overline{H}_{joint} represent the joint and view specific TUV and the mean TUV for the anatomically equivalent joint and view from the normative data set respectively, the macrophage contribution to TUV is MI_{joint}:

$$MI_{joint} = \frac{TUV_{joint} - \overline{H}_{joint}}{\overline{H}_{joint}}.$$

Step 4: TUV_{global} is the total of the macrophage-involved contributions for the IJs. (Note that MI_k is effectively 0 if TUV_{joint} is less than or equal to the upper limit of normal from the normative data set.) That is,

$$TUV_{global} = \sum_{All IJs} MI_{IJ},$$
$$TUV_{global} = \sum_{k=1}^{22} MI_k.$$

The change in TUV_{global} (Δ TUV_{global[5w]}) is the Δ % from baseline:

$$\Delta TUV_{global[5w]} = 100 \cdot \frac{TUV_{global[5w]} - TUV_{global[b]}}{TUV_{global[b]}}.$$

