4.0 Analysis of Efficacy

4.1 Description of Efficacy Variables

4.1.1 Definition of Responder/Non-Responder Status

4.1.1.1 Prediction Algorithms

The following two prediction algorithms will be defined for use in evaluating primary and secondary efficacy. Each algorithm will be used to predict a clinical response, and the subsequent prediction will be compared to the actual observed clinical response as described in Sections 4.1.2 and 4.1.3. In addition to these two prediction algorithms, the use of TUV_{global[b]} alone for the prediction of non-response will be analyzed as the key secondary efficacy variable. If TUV_{global[b]} is < 5 then the prediction is N (no improvement), otherwise, prediction is Y (improvement).

The $\Delta TUV_{global[5w]}$ values will be used to predict improvement at 12 and 24 weeks according to algorithm 1. The $\Delta TUV_{global[12w]}$ values will be used to predict improvement at 24 weeks according to algorithm 2. Both algorithms will be applied after the change in TUV calculations have been rounded to the nearest integer percentage (i.e., nearest hundredths place for a proportion).

1. ∆TUV_{global[5w]} bucketing

In the below, TUV_{global} represents the global TUV at the current time point and $TUV_{global[b]}$ represents the global TUV at baseline:

- If TUV_{global[b]} is < 5 then the prediction is N (No improvement)
- Else if

$$\Delta TUV_{global[5w]} = \frac{TUV_{global[5w]} - TUV_{global[b]}}{TUV_{global[b]}} \le -0.10$$

the prediction is Y (patient has improved). That is, a patient will be predicted as improved if TUV_{global} goes down by greater than or equal to 10%.

- Otherwise, the prediction is N.
- 2. $\Delta TUV_{global[12w]}$ bucketing

In the below, TUV_{global} represents the global TUV at the current time point and $TUV_{global[b]}$ represents the global TUV at baseline:

- If TUV_{global[b]} is < 5 then the prediction is N (No improvement)
- Else if

$$\Delta TUV_{global[12w]} = \frac{TUV_{global[12w]} - TUV_{global[b]}}{TUV_{global[b]}} \le -0.10$$

the prediction is Y (patient has improved). That is, a patient will be predicted as improved if TUV_{global} goes down by greater than or equal to 10%.

• Otherwise, the prediction is N.

Tables which display the concordance between the predictions from each algorithm vs. clinical assessment will be provided. A listing showing which algorithms provide a prediction of improvement vs. no improvement, by patient, will also be provided.

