Х	Improved	xxx (xxx%)	xxx (xxx%)	xxx (xxx%)	PPV	XXXX
					Confidence Limits	(XXXX, XXXX)
					p-value	X.XXXX
	Not Improved	xxx (xxx%)	xxx (xxx%)	xxx (xxx%)		
					NPV	XXXX
	Total	xxx (xxx%)	xxx (xxx%)	xxx (xxx%)	Confidence Limits	(XXXX, XXXX)
					p-value	X.XXXX
					OA	XXXX
					Confidence Limits	(XXXX, XXXX)

 a p-values for PPV testing Ho: π = 0.65 and for NPV testing Ho: π = 0.7. STATKING Clinical Services (DD-MMM-YYYY) Source Program: xxxxxx.sas

Within each part, the above will be displayed for each reader. This format repeats for Part 2 (ACR50), Part 3 (ACR70), Part 4 (CDAI), Part 5 (DAS28), and Part 6 (HAQ-DI). Full table format repeats for PP population (table 22) and for tables 23 – 28.

Table 29. Kendall Rank Correlation of ΔTUV, ΔCDAI, ΔACR Response Criteria Components, and ΔDAS28 with ΔTUV at 5 Weeks Navidea Biopharmaceuticals - Study No. NAV3-33 ITD Population (N=xxx)

Part 1 of 3: Reader x

	Component		Kendall	95% Confidence			Standard
Measure ^a	Parameter	Time Point	Correlation ^b	Limits ^c	n	Mean	Deviation
Δ TUV		5 Weeks			XXX	XXXXXX	XXXXXX
Δ TUV		12 Weeks	X.XXX	(x.xxx, x.xxx)	XXX	XXXXXX	XXXXXX
		24 Weeks	x.xxx	(x.xxx, x.xxx)	XXX	XXXXXX	XXXXXX
Δ CDAI	Overall	5 Weeks	X.XXX	(x.xxx, x.xxx)	XXX	XXXXXX	XXXXXX
		12 Weeks	X.XXX	(x.xxx, x.xxx)	XXX	XXXXXX	XXXXXX
		24 Weeks	X.XXX	(x.xxx, x.xxx)	XXX	XXXXXX	XXXXXX
Δ CDAI	XXXXXXXX	5 Weeks	X.XXX	(x.xxx, x.xxx)	XXX	XXXXXX	XXXXXX
		12 Weeks	X.XXX	(x.xxx, x.xxx)	XXX	XXXXXX	XXXXXX
		24 Weeks	X.XXX	(x.xxx, x.xxx)	XXX	XXXXXX	XXXXXX
Δ ACR	XXXXXXXX	5 Weeks	X.XXX	(x.xxx, x.xxx)	XXX	XXXXXX	XXXXXX
		12 Weeks	X.XXX	(x.xxx, x.xxx)	XXX	XXXXXX	XXXXXX
		24 Weeks	x.xxx	(x.xxx, x.xxx)	XXX	XXXXXX	XXXXXX
Δ DAS28		5 Weeks	X.XXX	(x.xxx, x.xxx)	XXX	XXXXXX	XXXXXX
		12 Weeks	x.xxx	(x.xxx, x.xxx)	XXX	XXXXXX	XXXXXX
		24 Weeks	x.xxx	(x.xxx, x.xxx)	XXX	XXXXXX	XXXXXX

^a Change in ACR will be evaluated through the following components of the ACR Response Criteria: swollen joint count, tender joint count, patient assessment, physician assessment, pain scale, disability/functionality questionnaire, and acute phase reactant (ESR).

 $^{
m b}$ Kendall rank correlation between Δ TUV at 5 weeks and the indicated measurement and time point.

 $^{\circ}$ Confidence limits calculated using Fisher's Z-transformation.

STATKING Clinical Services (DD-MMM-YYYY)

Source Program: xxxxxx.sas

Table format is repeated for each reader. Entire table (all parts) is repeated for the PP population (table 30).

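### The ΔTUV-with-ΔTUV rows of SAP Tables 29 to 32 share one baseline scan, so zero is the wrong reference for their printed 95% intervals

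*SAP*

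**What the plan says.** SAP 2.5 gives the Week 5 change in global uptake as a percentage: it "is the Δ % from baseline", with the baseline TUV_global both subtracted and used as the denominator. SAP 4.1.1.1 uses the same form for Week 12, where the denominator "represents the global TUV at baseline". No separate formula is given for Week 24; I assume the same form.

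The footnote to Table 29 in SAP Appendix B takes ΔTUV "TUV at 5 weeks and the indicated measurement and time point" as the pair for each Kendall correlation. The rows cover ΔTUV at Weeks 12 and 24 as well as the changes in CDAI, ACR components and DAS28. Table 31 has the same layout with Week 12 as the reference visit, so its one ΔTUV correlation is Week 12 with Week 24. Tables 30 and 32 repeat these for the per-protocol population, and all four tables are produced for each reader. On the intervals, the shells say only: "Confidence limits calculated using Fisher's Z-transformation". The variance to be used for Kendall's tau is not stated. The ΔTUV rows carry no null value, p-value or caveat.

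The text of SAP 4.2.3 plans Kendall correlations only between ΔTUV at Week 5 and clinical changes. The monitoring objective in SAP 1.0 likewise pairs TUV change "and changes in clinical RA assessments as a means to monitor therapy". The ΔTUV-with-ΔTUV rows exist only in the table list and shells.

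Protocol 8.4.1 now places imaging after "injection at Visits 2 and 4", that is, at Day 0 and Week 5. According to the protocol synopsis, "Tilmanocept will also be administered to a subset of subjects at weeks 12 and 24": those who completed these visits before Amendment 4 was activated. The size of that subset is not given.

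**The concern.** Two changes measured from one baseline are correlated by construction. If a patient's baseline scan reads too high by chance, both later changes look like falls. If it reads too low, both look like rises. This happens even when uptake never moved and the follow-up scans are unrelated to each other.

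A correlation printed with a 95% interval and no reference value will usually be read against zero. Here that reading would turn a property of the calculation into apparent evidence that an early change in uptake persists. The rows would also repeat the artefact: 2 correlations in Table 29 and 1 in Table 31, for 3 readers and 2 populations, make (2 + 1) × 3 × 2 = 18 printed values, all exposed to the same error. Agreement among them could pass for replication.

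**Working it through.** The documents state no tau, null value or n for these rows, so there is no planned figure to reproduce.

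**Inputs**
- Definition of change: SAP 2.5 and 4.1.1.1, assumed to hold for Week 24.
- Interval: 95%, Fisher's Z (table shells). Variance constant not stated; I show two choices.
- Repeatability of TUV_global: not in the documents. Assumed independent between visits, with a range of error-variance ratios.
- Number with Week 12 and 24 scans: not in the documents. The whole study is planned so that "198 to 672 evaluable subjects may be enrolled"; the subset can only be smaller than the number enrolled.

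**Step 1: tau from noise alone.** Write the observed value at visit t as T·exp(e_t), with T constant for the patient and e_t independent and identically distributed over visits. Percent change ranks patients exactly as e_t − e_b does. Take two patients and let D_b, D_5 and D_12 be the differences in their errors at each visit. The pair is concordant when D_5 − D_b and D_12 − D_b have the same sign, that is, when D_b is the smallest or the largest of three exchangeable quantities. That has probability 2/3, so

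tau = 2 × (2/3) − 1 = 1/3.

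Normality is not needed. Under normal errors the check is rho = 0.5 and tau = (2/π)·arcsin(0.5) = 0.333. Simulation with multiplicative, additive, heavy-tailed and uniform errors gave 0.331 to 0.338. A simulated 22-joint, two-view sum above a limit of normal, as in SAP 2.5, gave 0.30 to 0.34.

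**Step 2: unequal errors.** Let k be follow-up error variance divided by baseline error variance. On the log scale with normal errors, rho = 1/(1 + k) and tau = (2/π)·arcsin(rho).

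| k | rho | tau |
|---|---|---|
| 0.25 | 0.80 | 0.59 |
| 0.5 | 0.67 | 0.47 |
| 1 | 0.50 | 0.33 |
| 2 | 0.33 | 0.22 |
| 4 | 0.20 | 0.13 |

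**Step 3: true changes that vary but do not persist.** With equal error variances, and true log changes independent between visits with variance c times the error variance, rho = 1/(2 + c). For c = 1, rho = 1/3 and tau = 0.22. For c = 2, rho = 1/4 and tau = 0.16.

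**Step 4: the printed interval.** The limits are tanh(atanh(tau) ± 1.96·SE). For tau = 1/3, atanh(tau) = 0.3466. With SE² = 1/(n − 3):
- n = 30: −0.03 to 0.62
- n = 50: 0.06 to 0.56
- n = 100: SE = 1/√97 = 0.1015, limits tanh(0.3466 ± 0.199) = 0.15 to 0.50

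At an observed tau of exactly 1/3 the lower limit reaches zero at n = 35. With the Kendall-specific variance 0.437/(n − 4) it does so at n = 18.

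**Step 5: how often noise alone gives an interval wholly above zero** (2,000 simulated data sets per n, equal errors, no true change):

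| n | SE² = 1/(n − 3) | SE² = 0.437/(n − 4) |
|---|---|---|
| 20 | 22% | 59% |
| 30 | 43% | 78% |
| 50 | 75% | 95% |
| 100 | 99% | more than 99% |

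**The case against.** The strongest case on the other side is that nothing in the plan depends on these rows. They have no hypothesis, p-value or success rule. No objective or endpoint uses them, and SAP 4.2.3 does not describe them. That a reader will compare the interval with zero is a prediction about readers, not something the plan states. All of this stands. It limits the importance of the point, and it also makes deletion nearly free.

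Four stronger readings are tempting, and the documents do not support them.
- A reader might infer that the intervals are bound to exclude zero. That depends on n, and the subset with Week 12 and 24 scans has no stated size. At n = 20 to 30 the outcome is far from certain.
- A reader might infer that these rows are the only planned view of whether an uptake change lasts. Figures 1 to 5 plot ΔTUV over Weeks 5, 12 and 24, and Table 5 summarises TUV by study day and joint. The rows are only the planned correlations between visits.
- A reader might take 0.33 as the correct null and require the lower limit to exceed it. That value assumes equal errors and no true change. Steps 2 and 3 show the reference moving from 0.13 to 0.59 with the error ratio, and falling to 0.22 or 0.16 when true changes vary without persisting. All patients start a new anti-TNFα drug, so varying true change is plausible. A fixed bar at 0.33 could dismiss real persistence.
- A reader might suppose that all four tables concern Week 5. Tables 31 and 32 pair Week 12 with Week 24; the artefact is the same.

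**Conclusion.** The point holds for the ΔTUV-with-ΔTUV rows of Tables 29 to 32 and for nothing else. The shared baseline scan makes the expected tau positive without any persistent effect, so zero is not the no-association value for the printed interval. The size is 1/3 under equal independent errors with no true change. Elsewhere it depends on a repeatability figure that the documents do not give. It is positive in every case examined, but no single number can serve as the correct reference. How often the interval would mislead depends on the unstated number of patients with later scans.

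The rows against ΔCDAI, ΔDAS28 and the ACR components do not share the scan and are not affected. Sensitivity, specificity and the NPV of baseline TUV_global do not use these correlations. This is a small, real defect in descriptive output, best removed before the tables are produced.

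**What to change.** Delete the ΔTUV-with-ΔTUV correlations from Tables 29 to 32 and adjust the table titles. No stated objective, endpoint in SAP 4.1.4 or analysis in SAP 4.2.3 is lost, and the later scans exist only for a subset.

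If the rows are kept, add a footnote saying that both changes use the same baseline scan; that this alone induces a positive correlation, about 0.33 under equal errors and roughly 0.13 to 0.59 for error-variance ratios from 4 to 0.25, and lower if true changes vary without persisting; and that the interval must not be read against zero as evidence of persistence. State the variance used for the Fisher limits. Do not set 0.33, or any other fixed value, as a threshold.

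Leave the clinical rows as they are. The cost is an edit to four table shells, and the loss or qualification of a few descriptive results.
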